3.8 Angiographic Imaging

At screening, perform a DSA to define the angio-architecture of the occluded vascular segment. While a DSA to define the angio-architecture of the occluded vascular segment is preferred, CTA or MRA is an acceptable substitute.

When possible, an assessment of collateral blood flow by DSA should be done per institutional standard of care, particularly in cases of terminal internal carotid artery occlusion.

Prior to mechanical thrombectomy by the Penumbra Device, obtain a baseline TIMI/TICI scores by DSA. CTA or MRA is not an acceptable substitute for this assessment. The investigator shall make an initial assessment of TIMI/TICI flow in the target vessel territory.

TIMI/TICI scores are to be assessed after completion of the procedure by the Separator 3D. If necessary, other components of the Penumbra System can be used at the discretion of the investigator with the TIMI/TICI scores recorded before and after each use. In the event that adjunctive treatments were used, TIMI/TICI scores should be assessed and recorded before and after each treatment. The TIMI/TICI scores after the use of the Penumbra System as well as after adjunctive treatments will be used for analysis.

Pre-procedure and post-procedure angiograms shall be sent to an unbiased Core Laboratory blinded to treatment allocation to make a final determination on TIMI/TICI flow.

3.9 Adjunctive Therapies and Protocol Deviation

If the Penumbra System with Separator 3D or the Penumbra System alone is unable to revascularize the target vessel to TIMI/TICI 2 or 3, use of other rescue therapies are considered a protocol deviation and must be reported in the Case Report Forms. Any use of IA tPA or other non-FDA-approved treatments for the purpose of reducing the clot burden will be considered a treatment failure. TIMI/TICI scores must be recorded before and after the use of rescue therapy.

3.10 Post-Procedure Evaluations

All patients will be assessed for 90 days from time of procedure.

A follow-up noncontrast CT scan will be performed at 24±12 hours after procedure, and will be reviewed to assess hemorrhagic transformation based on ECASS definitions^{21,22}:

- HI 1 (small petechiae along the margins of the infarcted area without space-occupying effect),

- HI 2 (more confluent petechiae within the infarcted area but without space-occupying effect),
- PH 1 (hematoma in $\leq 30\%$ of the infarcted area with some slight space-occupying effect),
- PH 2 (hematoma in $>30\%$ of infarcted area with substantial space-occupying effect).

In addition, any neurological deterioration should be evaluated by urgent CT scan and other evaluations as indicated according to investigator/hospital best practice.

A symptomatic intracranial hemorrhage will be defined as 24 \pm 12 hour CT evidence of an ECASS defined ICH and a 4-point or more worsening of the NIHSS score.

Patients will be evaluated for neurological and/or functional status immediately post-procedure, 7 days after procedure (or day of discharge from the hospital, whichever is earlier), 30 days (± 10 days), and 90 days (± 10 days) after procedure. The assessments shown in **Table 7** must be performed:

Table 7 – Schedule of Assessments

Assessment	Pre-Admission Evaluation	Baseline Evaluation	Immediate Post-Procedure	24 \pm 12 Hr Follow-Up	7 days Follow-Up or Discharge ^D	30 Days Follow-Up (± 10 days)	90 Days Follow-Up (± 10 Days)
History		√					
Physical Exam ^A		√			√	√	√
NCCT ^B		√		√			
TIMI/TICI Scores from Angiography ^C		√	√				
NIHSS		√		√	√	√	√
mRS	√	√				√	√
Lipids Profile					√		
Liver Enzymes		√			√		
BUN, Creatinine		√			√	√	
CBC/Platelets/INR/PT/PTT		√	√		√	√	
Pregnancy Test		√					
Adverse Events			√	√	√	√	√

A: Includes recording of supine blood pressure and heart rate

B: In addition to the evaluation at Admission, standard CT scans must be obtained within 24 \pm 12 hours post-procedure and immediately after any neurologic decline that occurs within 90-day follow-up

C: From digital subtracted angiography

D: Assessments can be done either at 7 days from procedure or at Discharge, whichever occurs sooner.

4. Assessment of Safety and Effectiveness

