4.3.3 Thrombectomy/Embolectomy

The risks of intra-arterial thrombectomy/embolectomy are similar to those associated with existing intra-arterial methods of recanalization. These risks include:

- allergic reaction and anaphylaxis from contrast media
- acute occlusion
- air embolism
- arteriovenous fistula
- death
- hematoma or hemorrhage at access site
- inability to completely remove thrombus
- infection
- intracranial hemorrhage
- ischemia
- kidney damage from contrast media

- device malfunction
- distal embolization
- emboli
- false aneurysm formation
- neurological deficits including stroke
- vessel spasm, thrombosis, dissection, or perforation

Risks directly associated with the Penumbra System and Penumbra Separator 3D are similar to the above. Considerable testing has been completed to ensure that the System does not pose a significant risk. Testing includes both *in vitro* and *in vivo* testing. In addition, the following will be performed to minimize the risks:

- Patients will be carefully evaluated before entering the study to ensure that the location of the occlusion and the time of stroke onset are appropriate for treatment with the Penumbra System.
- During the clinical study, the procedure will be performed in an Operating Room or in an angiographic suite with an Operating Room standby. Therefore, should complications arise requiring surgery or other interventions, the surgery or intervention can be initiated without delay. All sites will be carefully selected to ensure that either a stroke unit operating according to national stroke guidelines or a physician experienced in treating patients presenting with acute ischemic stroke is available.
- Patients will be carefully monitored during the study and the follow-up period. The Investigator will examine and perform various diagnostic tests before, during, and after the procedure, at 7 days or at hospital discharge, and at 30 days (± 10 days) and 90 days (± 10 days) after the procedure.
- In addition to monitoring data directly related to the Penumbra System, blood data will be obtained pre-operatively. This data will be used to determine the patients' coagulation status, to assess for infection as indicated by white blood cell count, and to detect significant internal bleeding with hemoglobin and hematocrit levels.

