10.2 Secondary Safety Analysis

The secondary safety variables:

- All cause mortality.
- Rate of symptomatic ICH

The proportion of patients in each group who experience a safety event based on these criteria will be calculated. The CEC/DSMB data supersede the investigator-reported data in all analyses Adverse Events. Rates of symptomatic and asymptomatic hemorrhage will additionally be provided. Frequency counts and percentage of patients within each category will be provided for categorical data. Estimates of the treatment differences and their 95% confidence intervals will be calculated. Subject rates will be compared between treatment groups with Fisher's exact test.

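### The symptomatic ICH definition leaves out bleeds in patients who die before the 12-36 hour CT and purely subarachnoid bleeds

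*Protocol*

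**What the plan says.** Protocol 2.2.2 lists the incidence of symptomatic intracranial haemorrhage as a secondary endpoint. Protocol 3.10 schedules a non-contrast CT at 24±12 hours, which "will be reviewed to assess hemorrhagic transformation based on ECASS definitions". Four grades follow: HI 1, HI 2, PH 1 and PH 2. Each is described relative to infarcted tissue; HI 1, for example, is "small petechiae along the margins of the infarcted area without space-occupying effect". Symptomatic ICH is then defined as 24±12 "hour CT evidence of an ECASS defined ICH and a 4-point or more worsening of the NIHSS score".

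The same section says that "any neurological deterioration should be evaluated by urgent CT scan and other evaluations as indicated according to investigator/hospital best practice", and note B to Table 7 requires a CT "immediately after any neurologic decline that occurs within 90-day follow-up". The definition does not refer to those scans.

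Protocol 4.3.3 names "vessel spasm, thrombosis, dissection, or perforation" among the risks of the procedure. SAP 10.2 lists "Rate of symptomatic ICH" as a secondary safety variable and gives no definition of its own, so the protocol wording governs.

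**The concern.** The definition has three joint conditions: a time window for the scan, a type of bleed and a change in NIHSS. A severe early bleed can fail the first and third because the patient does not live long enough to be rescanned and rescored. A bleed caused by perforating a vessel can fail the second because subarachnoid blood is not one of the four listed grades.

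Both gaps concern bleeding that a thrombectomy device trial would want to see. The symptomatic ICH rate will be reported by arm with a 95% confidence interval and a Fisher test, and readers will take it as the symptomatic bleed rate. If it leaves out some of the earliest or procedure-caused bleeds, it is too low. If those bleeds are not equally frequent in the two arms, the comparison is distorted as well.

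**Working it through.** **1. Each kind of bleed against the definition in Protocol 3.10.**

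| Patient | CT at 12-36 h shows the bleed | Listed ECASS type | NIHSS worse by 4 or more | Counted |
|---|---|---|---|---|
| Bleed at 3 h on urgent CT, death at 10 h | No scan in window | Possibly | No score at the 24±12 h visit | No |
| Early bleed on urgent CT, survivor, no later NIHSS | Possibly | Possibly | Not available | No |
| Purely subarachnoid bleed | Yes | No | Yes | No |
| Early ECASS-type bleed, survivor, still visible at 12-36 h | Yes | Yes | Yes | Yes |
| Urgent CT that itself falls at 12-36 h, ECASS type | Yes | Yes | Yes | Yes |

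**2. Whether another passage closes the gap.**

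- Protocol 11.3 defines intracranial haemorrhage broadly, as bleeding within the cranium, but Protocol 3.10 ties the symptomatic endpoint to the ECASS types.
- The core lab reads all scans for ICH (SAP 13.2). No rule carries a read from an urgent CT, or a subarachnoid read, into the endpoint.
- The CEC/DSMB adjudicates causality and attribution (SAP 13.1). It is given no rule for classifying an event as symptomatic ICH.
- No rule treats death as meeting the 4-point criterion.
- The reference score for the worsening is not stated. Table 7 schedules NIHSS at baseline and then at 24±12 hours, with none marked immediately after the procedure.
- Protocol 9.4.2 and SAP 10.2 add rates of asymptomatic haemorrhage, but neither defines that category. The uncounted bleeds could fall into it or into none.

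**3. Size per event.** The documents give no expected count, no power and no missed share for symptomatic ICH. The only plan figure needed is the group size: 103 / (1 − 0.10) = 114.4, rounded up to 115, which agrees with Protocol 9.1 and SAP 3.2.

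- One uncounted event: 1 / 115 = 0.9 percentage points.
- Four uncounted events: 4 / 115 = 3.5 percentage points.

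The range of 1 to 4 events is an assumption for illustration only.

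**4. Effect on the difference.** Let p be the true symptomatic bleed risk in an arm and u the risk of an uncounted bleed. The reported rate is p − u, so

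reported difference = (p_3D − p_C) − (u_3D − u_C).

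- Two uncounted events in each arm: each rate is low by 2 / 115 = 1.7 points, and the difference is unchanged.
- Four in one arm and none in the other: the difference is wrong by 3.5 points.
- The error is towards no difference if the excess of uncounted bleeds is in the arm with more bleeding (and is no larger than the true difference). It exaggerates the difference if the excess is in the other arm.

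**The case against.** The strongest reply is that these bleeds leave one rate, not the trial. A bleed that is serious, judged related to device or procedure, and within 24 hours counts in the primary safety endpoint, which is compared between arms on CEC/DSMB-adjudicated data. A fatal bleed counts in all-cause mortality. SAP 2 rests study success on TICI non-inferiority alone and keeps secondary endpoints out of success and product claims. The ECASS grading is a cited choice that helps comparison with earlier trials. All of this stands, and it limits the consequence. It does not close the gap: neither of the other endpoints isolates bleeding, and the first depends on attribution.

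Three stronger readings are tempting, and the documents do not support them.

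- **Every bleed seen before 12 hours is lost.** A reader might infer this. A survivor whose ECASS-type bleed is still visible at 12-36 hours, with the NIHSS worsening, is counted.
- **The comparison is biased towards no difference.** That holds only under the condition in step 4 of the working. The documents give no evidence that uncounted bleeds would differ between arms.
- **The loss can be scaled from the 11.2% rate of the sponsor's pivotal study.** One could compute 0.112 × 115 = 12.9 events and remove a share. The protocol does not say how that study defined symptomatic ICH. If it used a similar definition, 12.9 is the number already counted and missed events would come on top. No missed share is given either.

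**Conclusion.** The point holds as a classification gap in a secondary safety endpoint. Read literally, Protocol 3.10 does not count as symptomatic ICH a bleed on an urgent CT in a patient who dies before the 12-36 hour CT or has no later NIHSS, nor a purely subarachnoid bleed. Nothing in the SAP extends the definition.

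Any such event makes the reported rate too low. The number is unknown: the 0.9 to 3.5 points per arm rests on an assumed 1 to 4 events among 115 patients and is not an estimate. An error in the between-arm difference needs the further assumption that uncounted bleeds are unequally distributed. The gap affects how safety is read, not whether the trial meets its success criterion.

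**What to change.** State one definition in both Protocol 3.10 and SAP 10.2, with these elements:

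- **Blood:** intracranial haemorrhage read by the core lab, of an ECASS type, subarachnoid or intraventricular.
- **Scan:** any CT from the procedure to 36 hours, including the urgent CTs already required.
- **Symptom:** a worsening of 4 points or more from a named reference NIHSS, for example the last value before the decline. Under Table 7 that will often be the baseline score, so the text should say so.
- **Death:** death within the same 36 hours that the CEC/DSMB attributes to the bleed. The time limit and the attribution keep a trivial petechial bleed with an unrelated death from counting.

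Report parenchymal and subarachnoid types separately by arm, and keep the current definition as a sensitivity analysis. Bleeds first seen after 36 hours stay outside, as now; the SAP should say that this is intended.

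The cost is mainly wording, because the scans and core-lab reads are already required. The core-lab form must record bleed type, and the case report form must hold an NIHSS taken at the decline. Since the sponsor's clinical team is not blinded (SAP 3.4), the change should be dated and made before bleeding is reviewed by arm. The downside is a slightly higher reported rate and less comparability with earlier trials, which the sensitivity analysis preserves.

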2.2 Study Objectives/Endpoints

The purpose of this study is to assess the safety and effectiveness of the Separator 3D as a component of the Penumbra System in the revascularization of patients presenting with acute ischemic stroke secondary to intracranial large vessel (≥ 2.5 mm in diameter) occlusion.

2.2.1 The primary endpoints are:

- Angiographic revascularization of the occluded target vessel at immediate post-procedure as defined by a TICI score of 2 or 3
- Incidence of device-related and procedure-related serious adverse event within 24 hours post-procedure

2.2.2 The secondary endpoints are:

- Good clinical outcome at 30 days post-procedure as defined by a 10 points or more improvement in the NIHSS at Discharge, a NIHSS score of 0-1 at Discharge; or a 30-day mRS score of 0-2.
- The proportion of patients with a modified Rankin Scale (mRS) score of ≤ 2 at 90 days post procedure.
- Good neurological outcome at 90 days post-procedure as defined by an mRS score of ≤ 2 , or equal to the pre-stroke mRS score if the pre-stroke mRS score was higher than 2, or an 10 or more points improvement on the NIHSS score.
- All cause mortality
- Incidence of symptomatic intracranial hemorrhage

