9.2 Statistical Analysis

The objective of the statistical analyses is to support the demonstration of the safety and effectiveness of the Penumbra System with Separator 3D. The efficacy analysis will be conducted in the intent-to-treat (ITT) and per protocol (PP) populations and the safety analysis will be conducted in the safety population. The specific details of the statistical analyses will be described completely in the statistical analysis plan. The statistical analysis plan will be finalized prior to database lock.

Descriptive statistics will be provided. This includes the number of observations, mean, median, standard deviation, minimum and maximum for continuous variables and counts and percents for discrete variables. Analyses will be conducted using SAS (SAS Institute, Cary, NC).²⁴

Results collected at multiple visits will be summarized at each visit for which they are collected as described in **Table 7**. Summaries for all measures will include all observed data for each visit.

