9.3.2 Secondary Effectiveness Endpoints

The secondary effectiveness variables:

- Good clinical outcome at 30 days post-procedure. Patients meeting one of the following are evaluated as having good clinical outcome: 10 points or more improvement in the NIHSS at Discharge; a NIHSS score of 0-1 at Discharge; 30-day mRS score of 0-2.
- Good neurological outcome at 90 days post-procedure. Patients meeting one of the following are evaluated as have a good neurological outcome at 90 days:
 - mRS score ≤ 2 at 90 days
 - mRS score at 90 days equal to the pre-stroke mRS score (if the pre-stroke mRS score was higher than 2)
 - 10 or more points improvement on the NIHSS score at 90 days
- The proportion of patients with a modified Rankin Scale (mRS) of ≤ 2 at 90 days post procedure.

Frequency counts and percentage of patients within each category will be provided for categorical data. Estimates of the treatment differences and their 95% confidence intervals will be calculated. Patient rates will be compared between treatment groups with Fisher's exact test.

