9.2 Secondary Effectiveness Analysis

The secondary effectiveness variables:

- Good clinical outcome at 30 days post-procedure. Patients meeting one of the following are evaluated as having good clinical outcome: 10 points or more improvement in the NIHSS at Discharge; a NIHSS score of 0-1 at Discharge; 30-day mRS score of 0-2.

- Good neurological outcome at 90 days post-procedure. Patients meeting one of the following are evaluated as having a good neurological outcome at 90 days:
 - mRS score ≤ 2 at 90 days
 - mRS score at 90 days equal to the pre-stroke mRS score (if the pre-stroke mRS score was higher than 2)
 - 10 or more points improvement on the NIHSS score at 90 days
- The proportion of patients with a modified Rankin Scale (mRS) of ≤ 2 at 90 days post procedure.

Frequency counts and percentage of patients within each category will be provided for categorical data. Estimates of the treatment differences and their 95% confidence intervals will be calculated. Subject rates will be compared between treatment groups with Fisher's exact test.

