10.5 Analysis of Deaths

The Kaplan-Meier product-limit method will be the primary method utilized to assess the mortality rate. With the date of procedure set at Day 0, any death occurring on or before calendar day 90 will be counted as a death. If clinical assessment is missing for a patient who has not died, the patient will be censored at the last follow-up date. Patients who are alive at day 90 will be censored at day 90. The log-rank test will be used to compare the groups. This comparison weights earlier and later differences equally. The time to death will be plotted with confidence intervals at monthly intervals.

Additionally, the death data will be presented as 90 Day binary deaths. The number of deaths will be presented for each group.

11 Pooling Across Centers

The clinical study will be conducted under a common protocol for each investigational center with the intention of pooling the data for analysis. Every effort will be made to promote

consistency in study execution at each investigational center. Analyses will be presented using data pooled across centers. Appropriate stratification and multivariate techniques, including contingency tables and logistic regression for binary outcomes, analysis of variance for continuous measures, and proportional hazards regression for time-to-event outcomes, will be used to assess differences between study centers to justify pooling data across centers. Centers with fewer than 10 patients will be combined and treated as one site in the pooling analysis.

12 Lost to Follow-Up and Missing Data

For sensitivity purposes, the following additional analyses will be conducted:

- Analyze only patients with complete primary endpoint data.
- For those patients without any observations after randomization, their final observations will be imputed by baseline scores and included in an analysis.
- A tipping point analysis will be conducted in which the missing data will be replaced with values such that the p-value is equal to the significance level.

13 Committees

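### The 30-day good clinical outcome takes two of its three limbs from an NIHSS read at day 7 or earlier discharge, so a patient who meets a limb early and then worsens or dies before day 30 still counts as a success

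*Protocol*

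**What the plan says.** SAP 9.2 counts a patient as having a good clinical outcome at 30 days if one of these is met: "10 points or more improvement in the NIHSS at Discharge; a NIHSS score of 0-1 at Discharge; 30-day mRS score of 0-2". Protocol 9.3.2 has the same three limbs. The endpoint list in Protocol 2.2.2 carries the 30-day label and the discharge reading in one sentence: "Good clinical outcome at 30 days post-procedure as defined by a 10 points or more improvement in the NIHSS at Discharge".

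The visit schedule is in Protocol 3.10. Its text places the follow-up examinations at "7 days after procedure (or day of discharge from the hospital, whichever is earlier), 30 days (± 10 days), and 90 days (± 10 days) after procedure", and footnote D of Table 7 repeats the rule: "D: Assessments can be done either at 7 days from procedure or at Discharge, whichever occurs sooner". Table 7 requires NIHSS at baseline, 24±12 hours, the day-7-or-discharge visit, 30 days and 90 days. It requires mRS at 30 and 90 days.

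The companion 90-day endpoint takes its NIHSS limb from the visit in its name: "10 or more points improvement on the NIHSS score at 90 days".

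**The concern.** There are two separate problems.

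- **Which reading.** The endpoint names a discharge reading, but the schedule stops at day 7 for anyone who stays longer. Neither document says that the discharge NIHSS in the endpoint means the combined day-7-or-discharge visit. Two analysts could score the same long-stay patient differently and both claim to follow the plan.
- **Which time.** Even if the reading is settled as the combined visit, it is taken no later than the scheduled day 7, while the endpoint is named for day 30. The limbs are alternatives, so an early success cannot be undone by later events.

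At stake is what the endpoint means. It is compared between arms with Fisher's exact test (SAP 9.2) and carried into the subgroup analyses (Protocol 9.3.3, SAP 9.4). Readers will take the reported rate as status at 30 days.

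**Working it through.** **The plan's own figure.** The only sample-size calculation is for the primary TICI endpoint. With 80% in both arms, a 15-point margin, one-sided alpha 0.05 and 85% power: n = (1.645 + 1.036)² × 2 × 0.80 × 0.20 / 0.15² = 102.3, so 103 per group (power 0.852). Then 103 / 0.90 = 114.4, so 115. It reproduces and is untouched by this point. The plan gives no expected rate or power for the 30-day outcome.

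**Definition against schedule.**

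| Limb | Reading named in the endpoint | Reading scheduled in Table 7 |
|---|---|---|
| NIHSS improved by 10 or more | Discharge | Earlier of day 7 and discharge |
| NIHSS 0-1 | Discharge | Earlier of day 7 and discharge |
| mRS 0-2 | 30 days | 30 days (±10) |

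**Following the rule as written.**

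1. A patient leaves on day 3 with an improvement of at least 10 points, then worsens or dies before day 30. The first limb is met, so the patient is a good outcome at 30 days. Neither the endpoint definition nor SAP section 12 lets a later death or decline override it.
2. A patient is in hospital past day 7, short of 10 points on day 7 but past that threshold on leaving, with a 30-day mRS above 2. On the day-7 reading this is a failure. On an unscheduled discharge reading, if the site took one, it is a success.
3. A patient has a 30-day mRS of 0-2. This is a success whichever NIHSS is used.

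**Whether another rule resolves it.** The imputation rule in SAP section 12 addresses a different case: "For those patients without any observations after randomization, their final observations will be imputed by baseline scores and included in an analysis". A long-stay patient has observations after randomization, so it does not apply. The rest of that section (a complete-case analysis of the primary endpoint and a tipping-point analysis) does not choose an NIHSS reading either.

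**Whether the 30-day NIHSS is used elsewhere.** The 90-day endpoint uses the 90-day value. Symptomatic ICH uses NIHSS worsening, but tied to the 24±12-hour CT: "hour CT evidence of an ECASS defined ICH and a 4-point or more worsening of the NIHSS score". What remains is descriptive: "Results collected at multiple visits will be summarized at each visit for which they are collected". No endpoint definition names the 30-day NIHSS.

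**Size.** The documents give no length of stay and no NIHSS course, so only a sensitivity range is possible.

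- Each patient reclassified in an arm of 115 moves that arm's rate by 1/115 = 0.87 points.
- For the ambiguous reading, let f be the assumed share of the 230 patients staying past day 7, and s the assumed share of those whose outcome depends on the reading chosen. Patients with a 30-day mRS of 0-2 add nothing to s. The overall rate moves by f × s.

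| f (assumed) | Patients without a scheduled discharge NIHSS | Shift for s = 5% to 20% (assumed) |
|---|---|---|
| 20% | 46 | 1 to 4 points |
| 40% | 92 | 2 to 8 points |
| 60% | 138 | 3 to 12 points |

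These are shifts in the overall rate. The difference between arms moves only if the shift differs by arm, and the documents give no basis for saying that it does.

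**The case against.** The strongest reply is that discharge is shorthand. The day-7-or-discharge visit is the only scheduled visit that carries the word, and every patient assessed there has an NIHSS. On that reading the endpoint can be computed for all of them and one clarifying sentence would do. The protocol and SAP name discharge consistently, so this may be a deliberate choice. The 30-day mRS limb gives every patient a route to success measured at the right time. Randomization is stratified by center (SAP 5.2), which helps to balance local discharge practice. Collecting a 30-day NIHSS for descriptive summary is not an error.

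Most of this stands, and it rules out several stronger readings that a reader might infer:

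- That long-stay patients fail both NIHSS limbs by default. No passage says so; they have a day-7 value and the mRS limb.
- That the endpoint is mostly settled in the first week. The documents do not give the share of successes arising from each limb.
- That a loss of power can be stated. The documents hypothesize no difference on this endpoint and give no misclassification rates.
- That the arms are biased against each other. Site staff are unblinded (SAP 3.4) and administer the NIHSS (Protocol 5.6), so influence is possible, but nothing shows it.

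What the reply does not answer is the time point. Reading discharge as the combined visit makes the endpoint computable, but a first-week success still stands as a 30-day outcome whatever happens next.

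**Conclusion.** The point holds as a mismatch between the endpoint's name, the reading it specifies and the schedule. It rests on the text alone: two limbs are not measured at 30 days, an early success cannot be reversed, and the reading for patients in hospital past day 7 is not stated. The ranges above rest on assumed values of f and s and only show how the rate would respond.

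The consequence is moderate. SAP section 2 keeps secondary endpoints out of study success and product claims, and the primary TICI analysis and both 90-day functional endpoints are unaffected. A reader might infer that the trial's conclusion is at risk; the documents do not support that.

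**What to change.** In Protocol 2.2.2 and 9.3.2 (and the synopsis) and in SAP 9.2, base both NIHSS limbs on the NIHSS at the 30-day visit, as the 90-day endpoint does with its own visit. Report the version based on the Table 7 day-7-or-discharge NIHSS as supportive, under the name of that visit. State in the SAP that death before the 30-day assessment counts as not having a good outcome, and how a missing 30-day NIHSS is handled. Renaming the limbs to the visit that Table 7 collects would remove the ambiguity but leave the time-point problem.

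The cost is wording in both documents and one extra table, with no new visit or test. There are two real downsides. It alters a prespecified secondary definition, so it should be made and documented before database lock, by which time the SAP is due to be final. It also makes the NIHSS limbs depend on attendance at the 30-day visit, although the mRS limb already does. A common visit removes the dependence of the reading day on length of stay, but it does not cure scoring by unblinded site staff.
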